3.6. Study outcomes

The study outcomes and endpoints are listed in Table 1.

[figure not shown]
Table 1. List of study outcomes and endpoints.

Outcomes	Endpoints
General information	
 ● Sex (male or female) ● Pregnancy mode (In vitro fertilization or not) ● Chorioamnionitis (Yes or not) ● GBS colonization (Yes or not) ● Early onset sepsis (Yes or not) ● Antenatal steroids (Yes or not) ● Delivery mode (natural delivery or cesarean section) ● Multiple births (Yes or not) ● Gestational age (weeks) ● Birth weight (grams) ● Mother's hemoglobin level before delivery ● Mother's HCT level before delivery
Neonatal morbidity and mortality	
 ● BPD ● ROP ● NEC ● Early onset sepsis ● Late onset sepsis ● EUGR ● IVH ● Death

4. Statistical analysis plan

Categorical variables were expressed as proportions n/N (%) and compared using the Chi-square (χ^2) test. Continuous variables were expressed as (mean \pm SD) or median and interquartile range (P25, P75), and compared using Student's t-test or a nonparametric test, as appropriate. Two-tailed p-values < 0.05 were considered statistically significant. A multivariate analysis by logistic regression was performed to evaluate predictors of neonatal morbidities. Statistical analyses were performed using IBM SPSS Statistics, version 20.

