Project BA2023

study protocol and statistical analysis

plan

Title: Analyses of Anemia Risk Factors and Prognosis in VLBW Infants.

Study center

Shenzhen Bao'an Women's and Children's Hospital (ShenzhenBMCHH)

Shenzhen Longhua Women's and Children's Hospital

Time frame

Study Start: March 1, 2023

Study Completion: March 24, 2024

1. Background

Preterm infants (accounts for 9.9% of newborn infants in 2020) are born with immature organs and immune system[1]. Especially, 4% of them are extremely preterm infants with a gestational age of less than 28 weeks[2]. In recent years, the treatment and management of extremely preterm infants has become the main task of NICU. Moreover, the morbidity rate for extremely premature infants around the world has been rising annually. These vulnerable patients are prone to various complications. Anemia is one of the most common complications that occur during hospitalization in these infants[3]. Therefore, According to a survey by the Canadian Neonatal Network (CNN), over 75% of extremely preterm infants receive at least one blood transfusion treatment during hospitalization[4], and WhyteRK et al.[5] even pointed out that over 90% of extremely preterm infants require blood transfusion treatment during hospitalization. Most of the recipients of blood transfusions are caused by anemia, indicating a very high incidence and severity of anemia in these immature infants. Anemia of prematurity (AOP) can cause a series of adverse consequences such as apnoea, prolonged mechanical ventilation, prolonged hospital stay, necrotizing enterocolitis (NEC) [6], retinopathy of prematurity (ROP) [7], infection, and extrauterine growth restriction (EUGR). It can be seen that anemia in premature infants, especially in extremely preterm infants, has a significant impact on their prognosis.

There is a lack of evidence regarding the relationship between blood hemoglobin level at birth and the neonatal morbidity and mortality of preterm infants despite the mode of delivery and prenatal infection. It remains unknown the impact of early anemia on the neonatal morbidity and mortality of extremely preterm infants[8]. With this study, We hope to demonstrate the relationship between anemia on admission to the neonatal intensive care unit (NICU) and the neonatal morbidity and mortality in extremely preterm infants.

2. Objective and hypotheses

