Objective: To study the risk factors of anemia in different stages of extremely preterm infants and their impact on prognosis, which provide a certain evidence for improving the prognosis of these infants.

Hypothesis: Small gestational age and low birth weight are risk factors for anemia and receiving blood transfusion treatment in extremely preterm infants. The younger the gestational age and the lower the birth weight, the more severe the anemia, and the greater the likelihood of receiving blood transfusion treatment.

3. Study design

3.1. study subject

From January 1, 2020 to December 31, 2022, extremely preterm infants with a gestational age of less than 28 weeks were admitted to Bao'an Women's and Children's Hospital affiliated with Jinan University and Longhua District Women's and Children's Hospital.

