3.3. Inclusion criteria

Extremely preterm infants with admission age \leq 24 hours, hospital stay \geq 14 days, and gestational age less than 28 weeks were included.

Anemia of Premature (AOP):

- Within 2 weeks of birth, venous blood hemoglobin level (Hb) \leq 130g/L, capillary blood \leq 145g/L.
- Age 2 weeks to 1 month, Hb $<$ 110g/L.
- Age after one month, Hb $<$ 90g/L.

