3.5. General information

Several variables on mother, pregnancy, delivery, resuscitation, hematologic parameters including the Hct and Hb at admission, PRBC transfusions, use of vasopressor agents within the first 72 h of life, data on invasive and noninvasive respiratory support, neonatal morbidity and mortality, and length of NICU stay were collected and analyzed.

Care practices included antenatal steroid use, the use of antenatal magnesium sulfate, cesarean section, and delivery room resuscitation.

- Antenatal steroids: A full cycle of antenatal steroids was considered when at least 12 h had elapsed after the last dose of dexamethasone (four doses of 6 mg of dexamethasone given intramuscularly 12 h apart) administered to the mother [9].
- Antenatal magnesium sulfate was defined as the intravenous administration of magnesium sulfate to the mother during pregnancy at any time before delivery.
- Gestational age (GA) was determined according to the first day of the last menstrual period, an early prenatal ultrasound examination, and a physical examination of the infant after birth [10].
- Maternal chorioamnionitis was diagnosed clinically during pregnancy, labor, or delivery.
- Small for gestational age (SGA) was defined as a birth weight below the 10th percentile, based on the Fenton Growth Chart [11].
- Neonatal sepsis was diagnosed in the presence of clinical signs (fever; hypothermia; lethargy; tachypnea; apnea/bradycardia; cyanosis; and hypoglycemia not explained by other diagnosis), associated to at least two laboratory markers (thrombocytopenia; leukocytosis or leucopenia; C-reactive protein elevation; PCT; I/T) according to our National Program of Infection Control Guidelines [12]. Early-onset sepsis and late-onset sepsis were considered if diagnosed before and after the first 72 h of life, respectively.
- Intraventricular hemorrhage (IVH) was classified according to Volpe [13].

- Bronchopulmonary dysplasia (BPD) was defined according to the National Institute of Health [14]. For the analysis of this study, we considered BPD as the dependency for oxygen until 36 weeks of corrected age.
- Parenteral nutrition was used as soon as there was clinical stability, preferably since day one of life, starting with a volume of 70 ml/kg/day, with daily increments until 150 mg/kg/day by day seven of life. Incubator humidity is usually 70% during the first week.

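### Section 4 analyses infants as independent although multiple births are eligible; if co-siblings are both analysed, p-values for predictors they share are slightly to modestly too small.

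*Combined protocol and SAP*

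**What the plan says.** Section 3.3 applies its limits infant by infant: admission within 24 hours, a stay of at least 14 days, "and gestational age less than 28 weeks were included". The four exclusions in section 3.4 cover early transfer or discharge, hemorrhagic disease, malformation or chromosomal abnormality, and inadequate data. None concerns multiples.

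Table 1 in section 3.6 lists "Multiple births (Yes or not" among the general variables. It lists no mother or pregnancy identifier.

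Section 4 compares categorical variables by chi-square. Continuous variables are "compared using Student's t-test or a nonparametric test, as appropriate". It adds that "A multivariate analysis by logistic regression was performed to evaluate predictors of neonatal morbidities". The threshold is two-sided 0.05. No clustered method and no one-infant-per-pregnancy rule is named.

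The hypothesis in section 2 is that "Small gestational age and low birth weight are risk factors for anemia and receiving blood transfusion treatment". Section 3.5 dates gestation from the last menstrual period, an early ultrasound and "a physical examination of the infant after birth".

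**The concern.** Siblings from one pregnancy have the same mother, and their outcomes tend to be correlated. For a predictor that is the same for both, a second sibling adds less information than an unrelated infant would, but the tests in section 4 count it in full. The standard error is then too small and the p-value too low.

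The predictors concerned are those that siblings share wholly or largely: gestational age, chorioamnionitis, GBS colonization, antenatal steroids, delivery mode, and maternal hemoglobin and HCT. Gestational age matters most because it is one of the two hypothesised factors. It may be only largely shared, since one of its three sources is an examination of the individual infant.

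The hypothesis has anemia and transfusion as outcomes, while the logistic model in section 4 is for morbidities. Of the methods stated, only the univariable tests could therefore carry the hypothesis, and these are unclustered too. A yes/no field for multiple birth does not say who is whose sibling, and adding it as a covariate does not correct the standard errors.

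**Working it through.** **Inputs from the documents.** Two-sided alpha 0.05 (section 4), so the critical value is 1.960. The plan gives no sample size, power or event count, so it has no figure of its own to reproduce.

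**Assumptions, not in the documents.** f is the share of analysed infants whose co-twin is also analysed, and r is the within-pair correlation of the outcome. Central range (f, r): (0.2, 0.2) to (0.3, 0.4). Full range: (0.1, 0.1) to (0.4, 0.6). Pairs only, with the predictor distributed alike in pairs and singletons.

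**Formulas.** With c the within-pair correlation of the predictor:

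- Design effect: DE = 1 + f × r × c
- Shortfall of the naive standard error: 1 − 1/√DE
- True error of the nominal 5% test: 2 × [1 − Φ(1.960/√DE)]
- Corrected value of a reported p of 0.03: 2 × [1 − Φ(2.170/√DE)]

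**Fully shared predictor (c = 1).**

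| f, r | DE | SE too small by | True error | p = 0.03 becomes |
|---|---|---|---|---|
| 0.1, 0.1 | 1.01 | 0.5% | 5.1% | 0.031 |
| 0.2, 0.2 | 1.04 | 1.9% | 5.5% | 0.033 |
| 0.3, 0.4 | 1.12 | 5.5% | 6.4% | 0.040 |
| 0.4, 0.6 | 1.24 | 10.2% | 7.8% | 0.051 |

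**Partly shared predictors.** If gestational age correlates 0.8 within pairs, the central range is DE = 1 + 0.2 × 0.2 × 0.8 = 1.032 to 1 + 0.3 × 0.4 × 0.8 = 1.096, a true error of 5.4% to 6.1%. At c = 0.5, an illustration for a factor such as birth weight, it is 5.2% to 5.7%. Sex is also only partly shared: monozygotic siblings always have the same sex, others need not.

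**Multiple-birth indicator.** Here every pair lies on one side of the comparison, so the formula above does not apply. If all multiples are in complete pairs, DE = 1 + r × (1 − f). With f from 0.2 to 0.4 and r from 0.1 to 0.5, this runs from 1 + 0.1 × 0.6 = 1.06 to 1 + 0.5 × 0.8 = 1.40, a true error of 5.7% to 9.8%. IVF is tied to multiple birth and is partly affected in the same way.

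**Check by simulation under no effect** (shared normal predictor, outcome 30%, N = 100 or 200, 5,000 to 6,000 runs per setting). The t-test rejected 5.4–5.6% at (0.2, 0.2) and 7.7–8.6% at (0.4, 0.6). At (0.1, 0.1) it rejected 5.2–5.5%, not distinguishable from 5%. A separate logistic simulation (N = 200, outcome 40%, f = 0.3, r = 0.33, 4,000 runs) rejected 6.1% unclustered and 4.8% with cluster-robust errors.

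**Which remedy holds its level.** Section 1 cites sources in which "over 75% of extremely preterm infants receive at least one blood transfusion treatment during hospitalization" and in which "over 90% of extremely preterm infants require blood transfusion treatment during hospitalization", so untransfused infants may be few. At 90% transfused, the plain cluster-robust Wald test rejected 7.3–8.6% with N = 100 (about 10 untransfused) and 6.1–7.3% with N = 200 (about 20). Across ten settings with outcome rates of 30%, 75% and 90%, a mother-clustered score test stayed at 4.0–5.3% and a one-infant-per-pregnancy t-test at 4.5–5.4%.

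**The case against.** The strongest reply is that both quantities driving the size are assumed. A yes/no field does not show that two siblings from one pregnancy are both in the data. The 24-hour, 14-day and early-transfer rules can split a pair, and a sibling who enters alone forms no cluster. This stands: the point is conditional, and a count of sibling sets could close it.

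A reader might infer that a reported p of 0.03 for gestational age is really about 0.05. That needs the extreme corner (40% of infants in pairs, correlation 0.6) and a fully shared predictor. At the same corner, with gestational age correlated 0.8 or 0.9 within pairs, it becomes 0.047 or 0.049. The central figures are 0.033 to 0.040.

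The effect is also small beside the plan's multiplicity. Table 1 has 12 factors and 8 outcomes, and early-onset sepsis is in both lists, so there are 12 × 8 − 1 = 95 pairings. At 5% each that is 95 × 0.05 = 4.8 expected false positives if no association is real. At (0.2, 0.2) it is 95 × 0.0546 = 5.2, even if every factor were fully shared. This limits the priority but does not remove the error.

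Finally, section 4 specifies no test of gestational age against anemia or transfusion, so the link to the hypothesis is inferred. That is correct. The inference rests on the fact that every method section 4 does name assumes independence.

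**Conclusion.** The point holds as a conditional one. Multiples are eligible and expected, no rule keeps one infant per pregnancy, and no stated method allows for siblings. If co-siblings are both analysed, tests of predictors they share are slightly to modestly anti-conservative: about 5.5% to 6.4% in place of 5% under the central assumptions, and 5.1% to 7.8% over the full assumed range. For the multiple-birth indicator, and partly for IVF, inflation can be larger. For birth weight and sex it is smaller.

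The documents do not support the stronger conclusions that siblings are known to be in the data, that the gestational-age result is invalid, or that its significance would be lost. They also show no bias from pooling the two hospitals, which is a separate matter. Low to moderate priority.

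**What to change.** 1. Link siblings by a mother identifier and report the number of sibling sets with more than one included infant. If there are none, the analysis needs no change.
2. If there are any, use GEE or cluster-robust inference by mother for the shared predictors, including any test of gestational age against anemia and transfusion, and for the morbidity models. Add a sensitivity analysis with one infant per pregnancy.
3. Where the rarer outcome class is small (about 20 infants or fewer), use a mother-clustered score test or rely on the one-per-pregnancy analysis, because plain robust Wald tests over-reject there.

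The cost is modest. Section 3.2 says maternal and infant records were both used, so linkage looks feasible, though it is not stated. Section 4 is written in the past tense and completion is given as March 24, 2024, so some re-analysis is likely. Intervals become slightly wider. With pairs only, the one-per-pregnancy analysis drops half of the paired infants: 0.1/2 = 5% to 0.4/2 = 20% of the sample over the assumed shares.

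### Death is an outcome of the admission-anemia question, but the only multivariable model is for morbidities, so read literally death gets only an unadjusted chi-square test

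*Combined protocol and SAP*

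**What the plan says.** All references are to the combined protocol and SAP.

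- **Question.** Section 1 (Background) closes by setting out to show "the relationship between anemia on admission to the neonatal intensive care unit (NICU) and the neonatal morbidity and mortality in extremely preterm infants".
- **Endpoint.** Table 1 (section 3.6) has an outcome row headed "Neonatal morbidity and mortality". It lists seven morbidities (BPD, ROP, NEC, early and late onset sepsis, EUGR, IVH) and then Death as a separate item.
- **Tests.** Under section 4, categorical variables are "compared using the Chi-square (χ^2) test". Continuous variables get a t-test or a nonparametric test.
- **Model.** Section 4 has one multivariable analysis: "A multivariate analysis by logistic regression was performed to evaluate predictors of neonatal morbidities". It names no exposure, covariate or selection rule.
- **Gestational age and birth weight.** The hypothesis in section 2 is that "Small gestational age and low birth weight are risk factors for anemia and receiving blood transfusion treatment in extremely preterm infants", and it is graded: "The younger the gestational age and the lower the birth weight, the more severe the anemia".
- **Design and entry.** Section 3.2 describes a retrospective record review. Section 3.3 requires a hospital stay of at least 14 days.

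**The concern.** Death is binary. If the logistic model covers morbidities only, the one method left for death is the chi-square comparison of proportions. Nothing in a record review balances gestational age or birth weight between anemic and non-anemic infants, and the plan itself expects the anemic infants to be less mature and lighter. If immaturity also raises mortality, part or all of a crude difference in deaths would reflect immaturity.

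At stake is the answer on the gravest endpoint listed. Section 2 speaks of impact on prognosis, so an unadjusted difference in mortality could be taken as evidence that admission anemia worsens survival when it shows no such thing.

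**Working it through.** **Which analysis covers death?** Sections 1, 3.2 and 3.5 and Table 1 all pair morbidity with mortality. The model sentence in section 4 drops mortality. No adjusted analysis of death appears anywhere else. On the literal reading, death has the chi-square test and nothing more.

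**Is there a figure to reproduce?** No. The plan gives no sample size, number of deaths, mortality rate or prevalence of anemia. What follows is an illustration on assumed inputs.

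**Set-up.** Take two gestational-age strata, lower and higher. Let w be the share of infants in the lower stratum, a_L and a_H the anemia prevalences, and d_L and d_H the mortality rates. Anemia has no effect on death within either stratum, so the true odds ratio is 1.0.

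- Anemic: risk = [w·a_L·d_L + (1−w)·a_H·d_H] / [w·a_L + (1−w)·a_H]
- Not anemic: risk = [w·(1−a_L)·d_L + (1−w)·(1−a_H)·d_H] / [w·(1−a_L) + (1−w)·(1−a_H)]

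**Central case** (w = 0.5; anemia 60% and 30%; mortality 15% and 5%):
- Anemic: (0.5×0.6×0.15 + 0.5×0.3×0.05)/0.45 = 0.0525/0.45 = 11.67%
- Not anemic: (0.5×0.4×0.15 + 0.5×0.7×0.05)/0.55 = 0.0475/0.55 = 8.64%
- Crude odds ratio = (0.1167/0.8833)/(0.0864/0.9136) = 1.40

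**Weaker gradients** (w = 0.5; anemia 50% and 30%; mortality 12% and 6%):
- 0.039/0.40 = 9.75% against 0.051/0.60 = 8.50%; odds ratio 1.16

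**Stronger gradients** (w = 0.5; anemia 70% and 30%; mortality 20% and 5%):
- 0.0775/0.50 = 15.5% against 0.0475/0.50 = 9.5%; odds ratio 1.75

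**A wider set of assumptions** (w = 0.4):

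| Anemia, lower / higher | Mortality, lower / higher | Risk, anemic / not | Crude odds ratio |
|---|---|---|---|
| 30% / 20% | 15% / 10% | 12.5% / 11.8% | 1.06 |
| 60% / 20% | 20% / 8% | 16.0% / 11.0% | 1.54 |
| 70% / 20% | 30% / 5% | 22.5% / 10.0% | 2.61 |

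The crude odds ratio is above 1 in every case although the true value is 1.0. The direction follows from lower gestational age raising both anemia and death. The size depends on rates the plan does not give.

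**Would the plan's p < 0.05 rule be met?** Assume 200 infants. In the central case, 90 are anemic and 110 are not. The standard error of the difference is √(0.1167×0.8833/90 + 0.0864×0.9136/110) = 0.043, so the expected z is 0.030/0.043 = 0.70 and significance is reached about 11% of the time. In the stronger case (100 and 100), the standard error is 0.047, z is 0.060/0.047 = 1.29 and the figure is about 25%. A false-positive test is therefore not the likely result at that size, but the estimate is biased either way.

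**The case against.** The strongest reply is that the point rests on one word. Section 3.5 says that data on morbidity and mortality were both analysed, and Table 1 puts Death in the same row as the morbidities, so the model sentence may be shorthand for the whole row. That is possible. But the plan pairs the two terms elsewhere and lists Death separately, so the literal reading is the fairer one. If death was meant to be included, the same edit makes that clear.

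A second reply is that section 4 leaves the model unspecified for every outcome, so death is only one symptom. This stands. A reader might infer that the morbidity results are protected by adjustment for gestational age and birth weight. The documents do not support that: no covariate is named, and anemia is not named as the exposure. Death is worse off only in having no adjusted model at all.

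Third, a reader might infer that the plan says immaturity causes anemia, or that it treats gestational age and birth weight as determinants of death. It does neither. Section 2 hypothesises that they are risk factors for anemia, and their effect on mortality is stated nowhere. The confounding argument needs only an association with anemia and an effect on death, but the second part must be labelled an assumption.

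Fourth, a reader might infer that the plan will report a crude difference as an effect of anemia. It has no such rule; section 1 asks about a relationship, and significance is far from assured at the size assumed above. The misreading is possible, not certain.

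**Conclusion.** The concern holds in this form: death is an outcome of the admission-anemia question, no adjusted analysis of it is written, and the unadjusted comparison that remains is open to confounding by two variables the plan links to anemia.

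If lower gestational age and birth weight also raise mortality, the crude odds ratio is pushed upward, which is away from the null when anemia truly has no effect or a harmful one. The illustrative spurious odds ratio is about 1.2 to 1.75, and 1.06 to 2.61 over the wider set. All inputs are assumed, and the documents cannot narrow the range.

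It would go too far to conclude that adjustment settles the mortality question. Because a stay of at least 14 days is required, earlier deaths appear to be excluded. An adjusted model would describe only infants who meet that rule, and adjustment does not correct the selection. This should be changed before mortality results are interpreted.

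**What to change.** Amend section 4 as follows.

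1. Extend the outcome of the logistic regression from neonatal morbidities to neonatal morbidities and death.
2. Name anemia on admission as the exposure, derived from the admission Hb collected under section 3.5. Section 3.3 defines anemia in three age bands, so the text must say that the exposure is the admission value.
3. Force gestational age and birth weight into the death model, and likewise into the morbidity models.
4. Use penalised (Firth) logistic regression if deaths are few. The plan names SPSS version 20, so check that the method is available there or name other software.
5. Base any statement about anemia and mortality on the adjusted estimate and its interval, not on the chi-square test.
6. State that the mortality result applies to infants meeting the 14-day stay rule.

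No new data are needed. Death, gestational age and birth weight are in Table 1. Infant hemoglobin is not (the table has only the mother's values), but section 3.5 lists it among the data collected. The cost is a few sentences, a little more analysis work, possibly other software, and a wide adjusted interval if deaths are few.

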3.2. The method of study

This was a retrospective study on the maternal and infant clinical and electronic records. We analyzed the maternal and obstetrical data, demographics, as well as the neonatal morbidity and mortality diagnosed during hospitalization. The study was approved by the Ethics Committee of our institution.

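### Two hospitals are pooled with no hospital term or stratification specified, so differences between them can bias the associations with transfusion and morbidity by an unknown, possibly small, amount

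*Combined protocol and SAP*

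**What the plan says.** Section 3.1 defines the cohort by place and date: "From January 1, 2020 to December 31, 2022, extremely preterm infants with a gestational age of less than 28 weeks were admitted to" two named hospitals, "Bao'an Women's and Children's Hospital affiliated with Jinan University and Longhua District Women's and Children's Hospital". Section 3.2 gives the design: "This was a retrospective study on the maternal and infant clinical and electronic records". Nothing is randomized.

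The hypothesis in section 2 links smaller and less mature infants to anemia and to transfusion: "the lower the birth weight, the more severe the anemia, and the greater the likelihood of receiving blood transfusion treatment". The background adds a second aim, relating anemia at NICU admission to morbidity and death.

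The analysis in section 4 has two layers:

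- **Crude comparisons.** "Categorical variables were expressed as proportions n/N (%) and compared using the Chi-square" test; continuous variables are "compared using Student's t-test or a nonparametric test, as appropriate".
- **Regression.** "A multivariate analysis by logistic regression was performed to evaluate predictors of neonatal morbidities". No covariates are named, and no regression is planned with anemia or transfusion as the outcome.

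Neither admitting hospital nor admission year appears in section 3.5, Table 1 or section 4. Section 3.5 records red-cell transfusions, but the documents state no transfusion rule shared by the two hospitals.

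**The concern.** Transfusion is partly a decision by the treating unit, and it is one of the outcomes in the hypothesis. Suppose one hospital admits smaller infants and also transfuses more readily. Low gestational age and transfusion would then go together in the pooled data even if they were unrelated within each hospital. The same holds for anemia and morbidity if both are more frequent at one hospital. Gradients in opposite directions would hide a real association instead.

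The exposure to this bias is greatest for the main hypothesis. The only regression planned is for morbidities, so anemia and transfusion as outcomes are left to crude comparisons, with no adjustment for hospital or anything else.

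**Working it through.** **Inputs from the documents.** Two hospitals and admissions in 2020 to 2022 (section 3.1); retrospective record review (section 3.2); unstratified tests, a two-sided 0.05 level and one logistic regression without named covariates (section 4). The documents give no sample size, event count, effect size or rate by hospital, so there is no figure of the plan's own to reproduce.

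**Assumed inputs.** Two hospitals of equal size. A binary exposure (for example anemia) has frequency e₁ and e₂, and a binary outcome (for example a morbidity) m₁ and m₂. Exposure and outcome are independent within each hospital, so the true within-hospital odds ratio is 1.

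**Formula.** Collapsing over hospitals, and dropping the common factor of one half:

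- a = e₁m₁ + e₂m₂
- b = e₁(1−m₁) + e₂(1−m₂)
- c = (1−e₁)m₁ + (1−e₂)m₂
- d = (1−e₁)(1−m₁) + (1−e₂)(1−m₂)
- pooled odds ratio = ad / (bc)

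**Two cases in full.**

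- 30% vs 40% for both exposure and outcome: a = 0.09 + 0.16 = 0.25; b = c = 0.21 + 0.24 = 0.45; d = 0.49 + 0.36 = 0.85. Odds ratio = 0.2125 / 0.2025 = 1.05.
- 30% vs 60% for both: a = 0.09 + 0.36 = 0.45; b = c = 0.21 + 0.24 = 0.45; d = 0.49 + 0.16 = 0.65. Odds ratio = 0.2925 / 0.2025 = 1.44.

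**Range by the same formula.**

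| Exposure, hospital 1 vs 2 | Outcome, hospital 1 vs 2 | Pooled odds ratio |
|---|---|---|
| 50% vs 50% | 30% vs 50% | 1.00 |
| 30% vs 40% | 30% vs 40% | 1.05 |
| 30% vs 50% | 30% vs 50% | 1.19 |
| 30% vs 60% | 30% vs 60% | 1.44 |
| 20% vs 60% | 20% vs 60% | 2.00 |
| 30% vs 60% | 60% vs 30% | 0.69 |

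The first row shows the condition for bias: if exposure does not differ by hospital, pooling does not distort the odds ratio, however much the outcome differs.

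**Effect on the test.** A simulation under the same null (2000 runs per setting, equal-sized hospitals, two-sided 0.05; total N of 100 and 200 are assumptions) compared the pooled chi-square test with the hospital-stratified Mantel-Haenszel test.

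| Exposure | Outcome | N | Pooled false-positive rate | Stratified |
|---|---|---|---|---|
| 50% vs 50% | 30% vs 50% | 100 | 4.9% | 4.8% |
| 50% vs 50% | 30% vs 50% | 200 | 5.0% | 4.7% |
| 40% vs 60% | 30% vs 50% | 100 | 7.3% | 5.3% |
| 40% vs 60% | 30% vs 50% | 200 | 10.4% | 5.5% |
| 30% vs 70% | 20% vs 60% | 100 | 35.7% | 4.5% |
| 30% vs 70% | 20% vs 60% | 200 | 64.9% | 4.3% |

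The simulation error at a true 5% is √(0.05 × 0.95 / 2000) = 0.5 percentage points, so the stratified results are compatible with the nominal level. A 70:30 hospital split changes the pooled odds ratio only a little: 1.16 instead of 1.18 in the 40% vs 60% setting, and 1.88 instead of 1.96 in the 30% vs 70% setting.

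**The case against.** **The plan has not rejected a hospital term.** Section 4 names no covariates at all, and section 3.5 describes categories of variables, not a closed list. A reader might infer that the sponsor decided to leave hospital out, or cannot identify it. The documents support neither: they say only that no term is specified, and eligibility in section 3.1 is itself defined by hospital and admission date. What stands is that the crude tests are stated as unstratified, so following the plan as written leaves hospital uncontrolled.

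**The morbidities have common definitions.** A reader might infer that diagnoses of BPD, NEC, sepsis and ROP simply reflect each hospital's own practice. Section 3.5 gives one definition or classification for each, and section 3.3 gives hemoglobin cut-offs for anemia. Application may still vary between units, but the documents do not show that it does. That inference forms no part of this point, which rests on transfusion, case mix and event rates.

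**The figures are crude and assumed.** The odds ratios above come from 2×2 tables, whereas the quoted sentence concerns a multivariable model. Gestational age and birth weight are in Table 1 and may enter that model, which would remove part of the case-mix path. Odds ratios of 1.44 and 2.00 need gaps of 30 and 40 points in both exposure and outcome, between two hospitals in one city whose infants are all under 28 weeks. All of this stands: the illustration shows what pooling can do, not what it did here.

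**Nothing supports a particular time trend.** The documents give no rates by year and no change in practice over 2020 to 2022. That is reason to treat year as a sensitivity analysis, not as a required term of a fixed form.

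**Conclusion.** The point holds in a limited form. Two hospitals are pooled in a non-randomized record review, no hospital term or stratification is specified, and no common transfusion rule is stated. Pooled associations can therefore be biased if exposure and outcome both differ between the hospitals.

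The omission is certain; its consequence is not. A reader might take the larger odds ratios or false-positive rates as estimates for this cohort. They are not, because they follow from assumed gaps, equal hospital sizes, no within-hospital association and no adjustment for other covariates. The plausible effect runs from none upward. The gap matters most for anemia and transfusion as outcomes, where the plan offers only crude comparisons. It is worth correcting mainly because the correction is cheap and uses information that already defines who is in the study.

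**What to change.** 1. Carry admitting hospital into the analysis data set and include it as a fixed covariate in each logistic model for morbidity. With only two hospitals, a random hospital effect could not be usefully estimated.
2. Add a logistic model for anemia and one for transfusion, each with gestational age, birth weight and hospital. This brings the stated hypothesis under adjustment and handles the two continuous predictors, which stratified chi-square methods do not.
3. Report hospital-stratified (Mantel-Haenszel) results alongside the crude chi-square tests. The crude results can stay.
4. Examine admission year as a sensitivity analysis where event counts allow.

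The cost is SAP wording and one extra parameter per model for hospital, plus up to two more for three calendar years in the sensitivity analysis. No new infants are needed. The downside is less precision for rare outcomes. No event counts are stated, so whether each model can carry the added terms must be checked once the counts are known; where events are few, hospital should take priority over year.
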